### 7.3.3 FINAL STUDY VISIT

Subjects will be contacted by telephone within one week to determine if there are any ongoing adverse events. The termination form will be completed and subjects will be terminated from the study. The PI will record all reportable events with start dates occurring any time after informed consent is obtained until 7 (for non-serious AEs) or 30 days (for SAEs) after the last day of study participation.

---

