## 2.3 POTENTIAL RISKS AND BENEFITS

### 2.3.1 KNOWN POTENTIAL RISKS

The potential risks for adverse effects of the treatment procedure include but are not limited to blistering, burns, excessive edema or erythema, infection, scarring and post-inflammatory hyperpigmentation.

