#### 4.2.2 SECONDARY ENDPOINTS

### Safety objectives

Subject's assessment of discomfort and pain as measured by a 10 cm visual analog scale (VAS).

Subjects experiencing a treatment-related adverse event (AE).

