#### **Pre-Treatment**

Subjects will be instructed to avoid sun exposure of the target treatment areas for at least six weeks before treatment and to use broad spectrum sunscreen of no less than 30 SPF daily, replenishing it as often as needed throughout the course of the study and for six weeks after the treatment. In addition, tanning is to be strictly avoided. Subjects should not receive any treatment with a laser or other devices in the study treatment area throughout the course of this study and follow-up examinations.

Protective eye goggles will be worn by both the patient and site staff performing the treatment for the duration of the treatment session.

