## **Assessment**

The assessment of discomfort/pain based on the subject's report will be documented immediately (within 5 minutes) after treatment and before any subsequent treatment using the 10 cm VAS.

The investigator will examine the treated area and report immediate and short term response (30 minutes post-treatment) (pain during treatment, hemorrhage, burn, erythema, edema, purpura) using a 5 point scale: 1=none; 2=trace; 3=moderate; 4=marked; 5=severe.

The normal response to these treatments is transient erythema and edema. If any other side effects occur, as indicated in the protocol, they must be recorded. Subjects will be discharged from the clinic.

---

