### 8.2.3 EXPECTEDNESS

Expected adverse reactions are AEs that are common and known to occur for the study agent being studied. Expected adverse events in this study include pain, tenderness, purpura, persistent erythema, edema, burn, blistering, crusting, hyperpigmentation, hypopigmentation, scarring and potential for damage to hair follicles within the treatment area and subsequent loss of hair within the treatment area.

An AE or suspected adverse reaction is considered "unexpected" if it is not known to occur for the study agent being studied and at the specificity or severity that has been observed.

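### Safety comparison lists scarring, pigment change and hair loss, but nothing is scheduled after a call by day 7, although AE recording runs on to about day 14 or 37

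*Combined protocol and SAP*

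**What the plan says.** **Objective.** The Protocol Summary and 2.2 state that the safety of the LED device will be compared with that of the diode laser. The safety endpoints in 4.2.2 are the pain VAS and the number of subjects with a treatment-related AE. The endpoint names no particular effect. Section 8.2.3 lists the expected AEs, which include "hyperpigmentation, hypopigmentation, scarring and potential for damage to hair follicles within the treatment area and subsequent loss of hair". Section 2.3.1 lists among the known risks "infection, scarring and post-inflammatory hyperpigmentation".

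**Scheduled observation.** Under Assessment in 7.3.2 the investigator examines the treated area for the immediate response and again at 30 minutes. The graded items are pain during treatment, hemorrhage, burn, erythema, edema and purpura. Section 7.3.3 and the schedule in 7.3.6 then provide one telephone contact within a week, at which subjects are terminated from the study. The Summary places that call after one week.

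**Recording window.** Sections 7.3.3 and 8.3 have the PI record events from consent "until 7 (for non-serious AEs) or 30 days (for SAEs) after the last day of study participation".

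**Other routes.** An AE found at an unscheduled visit goes on the AE form (7.3.5). Known events are followed to resolution or stabilization (8.3). Subjects with a device complication are followed for at least two years, and minor complaints can be reported within 30 days of the complaint (7.8).

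**The concern.** Three parts of the plan do not fit together: the effects it lists, the period over which it says it will record them, and the points at which anyone looks or asks. No scheduled procedure checks the treated skin for scarring, pigment change or hair loss, and most of the recording window after treatment contains no contact.

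What is at stake is how an absence of events would be read. If these effects usually begin after the call, no reports on either flank would be the likely outcome whether the true risk is low or moderate. Reported as a safety comparison, that would look like evidence that the two devices are alike on these effects, when the observation could hardly have shown otherwise.

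**Working it through.** The plan states no detection or power figure for safety, so there is nothing to reproduce. Three checks follow.

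**1. Day arithmetic.** Day 0 is treatment, and the call is taken as the last day of participation.

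| Call on | Non-serious window ends | SAE window ends | Scheduled contacts after the call |
|---|---|---|---|
| day 7 | 7 + 7 = day 14 | 7 + 30 = day 37 | none |
| day 1 (also within one week) | 1 + 7 = day 8 | 1 + 30 = day 31 | none |

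**2. Share of events that start by the call.** The documents give no onset times, so the medians are assumptions. For median m, the share with onset by day t is Φ(ln(t/m)/s) for a log-normal with s = 0.5 or 0.8, and 1 − 2^(−t/m) for an exponential. Example for m = 14 and t = 7: Φ(ln 0.5/0.5) = 8.3%, Φ(ln 0.5/0.8) = 19.3%, and 1 − 2^(−0.5) = 29.3%.

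| Assumed median onset | By day 7 | By day 37 |
|---|---|---|
| 3 days | 80-96% | over 99% |
| 7 days | 50% | 97% or more |
| 14 days | 8-29% | 84-97% |
| 28 days | 0.3-16% | 60-71% |
| 42 days | 0-11% | 40-46% |
| 90 days | 0-5% | 4-25% |

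With a day-1 call, the share is at most 5% for any median of 14 days or more. These are shares that have begun. The share a subject would notice and mention by telephone cannot be larger.

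**3. What 10 subjects could show.** Let p be the true risk per subject for one device (assumed) and f the share captured. The chance of at least one event in 10 is 1 − (1 − pf)^10.

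| p | f = 1 | f = 0.50 | f = 0.25 | f = 0.05 |
|---|---|---|---|---|
| 5% | 40.1% | 22.4% | 11.8% | 2.5% |
| 10% | 65.1% | 40.1% | 22.4% | 4.9% |
| 20% | 89.3% | 65.1% | 40.1% | 9.6% |

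For p = 10% and the 14-day median (f = 0.083 to 0.293), the chance is about 8% to 26%, against 65% with full capture.

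If 0 of 10 subjects have an event, the one-sided 95% upper bound on risk is 1 − 0.05^(1/10) = 25.9% with full capture. Allowing for capture, it is 25.9%/f: about 52% at f = 0.50, and above 100%, hence uninformative, at f = 0.25 or below.

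**The case against.** The best reply is that this is a feasibility study of up to 10 subjects, with temperature as the primary endpoint, a declared participation of one day plus a call, and descriptive AE counts only. Even perfect capture leaves an upper bound near 26% after zero events, so an extra call would not make the comparison precise, and a call is not an examination. All of that is true. It limits how much can be concluded, but it does not explain why the plan opens a recording window and schedules nothing in it.

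Several stronger readings are tempting, and the documents do not support them.

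- *The protocol calls these effects late.* It does not. Only hair loss is described as subsequent, and no onset time is given. With a median onset of 3 days, most events would have begun by a day-7 call.
- *Sun protection "throughout the course of the study and for six weeks after the treatment" shows how long the skin is thought to be at risk, so a 7-day follow-up can be set against 42 days.* The same section also asks for sun avoidance for six weeks before treatment and gives no reason for either period. The ratio does not measure missed events.
- *Later events could not be recorded at all.* Sections 7.3.5, 7.8 and 8.3 leave routes open. A burn or blister seen on the day or reported at the call would be followed, so a resulting scar could be observed. Section 8.1.2 makes permanent impairment of body structure serious, so a lasting scar might fall in the 30-day window. What stands is that each route needs the subject to come forward or the event to be known already.
- *The gap favours the LED device.* No events on both flanks is parity. The risk is an unsupported statement of similarity.

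**Conclusion.** The gap is real. The safety comparison takes in pigment change, scarring and hair loss through the expected-AE list. No scheduled examination looks for them, and no contact is scheduled in the 7 or 30 days of recording that follow the call.

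Its size depends on onset, which the documents do not give. With a typical onset of about two weeks or later, a day-7 call would come after at most 29% of events had begun, and zero events would say little about these risks. With onset within a few days, the loss is small. The calculation assumes log-normal or exponential onset, independent subjects and, for the detection figures, true risks of 5% to 20%. The schedule mismatch itself needs no assumption beyond the day of the call.

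**What to change.** **Preferred.** In 7.3.3, 7.3.6 and 8.3:

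- Add one telephone contact at the end of the existing 30-day SAE window, about day 37 if the first call is on day 7.
- Count both recording windows from the treatment day and close them at that contact. If they stay tied to the last day of participation, the new call would only push them out again.
- Extend non-serious AE recording to the same date.
- Ask specifically about pigment change, scarring and hair loss, separately for the left and right flank. Each flank receives a different device, and the AE summaries in section 10 count subjects, so without the side an event cannot be attributed to a device.
- Reconcile the timing of the first call between the Summary (after one week) and 7.3.3 and 7.3.6 (within one week).

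Under the same assumptions, the share begun by the last contact rises from 8-29% to 84-97% for a 14-day median, and from 0.3-16% to 60-71% for a 28-day median. Much slower effects would still be missed.

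The cost is one call for each of up to 10 subjects and participation of about five weeks instead of one, which may lengthen the two-month study. The information would be self-report without examination.

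**Wording only.** Restate the safety objective in the Summary, 2.2 and 3 as acute tolerability up to the follow-up call, and state that no conclusion will be drawn on the listed effects that may appear later. This costs nothing in conduct, but gives up any statement on those effects.

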### 7.3.4 EARLY TERMINATION VISIT

Subjects who terminate the study early for whatever reason, will be asked to provide a reason for their early termination. Adverse events and the reason for early termination will be recorded.

---

### 7.3.5 UNSCHEDULED VISIT

If an unscheduled visit occurs, the reason for the unscheduled visit will be documented. If the unscheduled visit is the result of an adverse event, the event will be recorded on the adverse event CRF.

---

### 7.3.6 SCHEDULE OF EVENTS TABLE

Procedures	Screening	Enrollment Baseline Visit 1, Day 1	Follow up Contact ≤ 7 days
Informed consent	X		
Inclusion/exclusion criteria	X	X	
Demographics	X		
Medical history	X		
Physical exam	X		
Vital signs		X	
Urine pregnancy test a	X		
Administer Treatment		X	
Temperature measurements		X	
Subject Discomfort/Pain VAS		X	
PI immediate & short-term response		X	
Concomitant medication		X	X
Adverse event evaluation		X	X

Telephone contact			X
a For women of child-bearing potential			

#### 7.4 JUSTIFICATION FOR SENSITIVE PROCEDURES

N/A

#### 7.5 CONCOMITANT MEDICATIONS, TREATMENTS, AND PROCEDURES

All concomitant prescription medications taken during study participation will be recorded on the case report forms (CRFs). For this protocol, a prescription medication is defined as a medication that can be prescribed only by a properly authorized/licensed clinician. Other medications to be reported in the CRF are concomitant over-the-counter medications and non-prescription medications.

#### 7.6 PROHIBITED MEDICATIONS, TREATMENTS, AND PROCEDURES

The use of immunosuppressive medications, anticoagulants and medications, herbal supplements, perfumes or cosmetics that may affect sensitivity to light are prohibited. The use of Accutane™ (Isotretinoin) within the past six months is also prohibited.

#### 7.7 PROPHYLACTIC MEDICATIONS, TREATMENTS, AND PROCEDURES

Apply a water-based spray to the treatment area prior to treatment.

#### 7.8 RESCUE MEDICATIONS, TREATMENTS, AND PROCEDURES

In the event that the subject experiences pain, the principal investigator may prescribe any analgesic deemed appropriate to the level of pain. If a subject experiences any first, second or third degree burn or pain beyond narcotics, then the following procedure will be implemented:

Immediate triage and treatment of the patient shall be determined by the treating physician and based upon severity and type of burn identified.

The event will be reported to the study Director within 24 hours of occurrence. If the event meets the criteria of a SAE, then it must be reported on the SAE form.

A copy of the patient chart and treatment parameters are to be forwarded to the study Director within 24 hours.

The study Director will be responsible for issuing a written report to the company and the IRB Chairman no later than 7 days from the incident.

Long term follow up and care shall continue at the discretion of the treating physician.

All patients experiencing a complication of the device will be followed a minimum of 2 years following the initial injury. Longer care and observation will be at the discretion of the treating physician.

All minor complications such as appearance or altered sensation, except for pain, can be reported within 30 days of patient complaint. Both chart and treatment parameters are to be provided to the study Director and shared with the company and IRB chairman.

## 8 ASSESSMENT OF SAFETY

### 8.1 SPECIFICATION OF SAFETY PARAMETERS

In addition to spontaneous reports of adverse events, subjects will complete a 10 cm discomfort/pain VAS and the principal investigator will examine the treated area and report immediate and short term response.

#### 8.1.1 DEFINITION OF ADVERSE EVENTS (AE)

Adverse event means any untoward medical occurrence associated with the use of an intervention in humans, whether or not considered intervention-related (21 CFR 312.32 (a)).

#### 8.1.2 DEFINITION OF SERIOUS ADVERSE EVENTS (SAE)

NOTE: The term serious is not synonymous with severity, which may be used to describe the intensity of an event experienced by the subject). An AE that does not meet any of the below criteria will be classified as non-serious.

A serious AE is any event that:

- Results in, or contributes to a death;
- Is immediately life threatening (injury or illness);
- Results in hospitalization, or prolongs an existing hospitalization;
- Results in permanent impairment of body structure or function, or in persistent or significant disability/incapacity;
- Results in an injury that requires medical intervention to prevent permanent impairment of body structure or function;
- Is a device malfunction or deterioration in the characteristics and/or performance of the device that results in death or serious deterioration in health;
- Is a device malfunction or deterioration in the characteristics and/or performance of the device that, if it were to occur again, could result in death or serious deterioration in health;
- Results in a congenital anomaly or birth defect.
- Is any medically significant injury, event or experience that requires medical/surgical intervention to prevent one of the outcomes listed above;
- Results in end organ toxicity, including hematological, renal, cardiovascular, hepatic, gastrointestinal, and central nervous system events;

#### 8.1.3 DEFINITION OF UNANTICIPATED PROBLEMS (UP)

This definition includes an unanticipated adverse device effect, any serious adverse effect on health or safety or any life-threatening problem or death caused by, or associated with, a device, if that effect, problem, or death was not previously identified in nature, severity, or degree of incidence in the investigational plan or application (including a supplementary plan or application), or any other

unanticipated serious problem associated with a device that relates to the rights, safety, or welfare of subjects (21 CFR 812.3(s)).

## 8.2 CLASSIFICATION OF AN ADVERSE EVENT

### 8.2.1 SEVERITY OF EVENT

For AEs not included in the protocol defined grading system, the following guidelines will be used to describe severity.

- **Mild** – Events require minimal or no treatment and do not interfere with the participant’s daily activities.
- **Moderate** – Events result in a low level of inconvenience or concern with the therapeutic measures. Moderate events may cause some interference with functioning.
- **Severe** – Events interrupt a participant’s usual daily activity and may require systemic drug therapy or other treatment. Severe events are usually potentially life-threatening or incapacitating.

### 8.2.2 RELATIONSHIP TO STUDY AGENT

The clinician’s assessment of an AE's relationship to the study agent is part of the documentation process, but it is not a factor in determining what is or is not reported in the study. If there is any doubt as to whether a clinical observation is an AE, the event should be reported. All AEs must have their relationship to study agent assessed. In a clinical trial, the study product must always be suspect. To help assess, the following guidelines are used.

- **Related** – The AE is known to occur with the study agent, there is a reasonable possibility that the study agent caused the AE, or there is a temporal relationship between the study agent and event. Reasonable possibility means that there is evidence to suggest a causal relationship between the study agent and the AE.
- **Not Related** – There is not a reasonable possibility that the administration of the study agent caused the event, there is no temporal relationship between the study agent and event onset, or an alternate etiology has been established.

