## PROTOCOL SUMMARY

TITLE	Feasibility Study of a 950 nm Wavelength LED Device for Non-invasive Lipolysis of the Flanks
SUMMARY	Open-label, feasibility study comparing the tissue temperature profile of a 950 nm LED device and a 1060 nm diode laser for non-invasive lipolysis of the flanks. The study will enroll up to 10 subjects requesting non-invasive lipolysis of the flanks. Each subjects will receive a single treatment with each device on opposite flanks. Tissue temperatures in the treated areas will be recorded and compared.
OBJECTIVES	The objective of this clinical study is to compare the tissue temperature profiles of the LED device and diode laser device and to compare safety in the treatment of lipolysis of the flanks.
ENDPOINT	Primary objective 

• Temperature profile comparison at various tissue depths.

 Safety 

• Subject's assessment of discomfort and pain as measured by a 10 cm visual analog scale (VAS).

• Subjects experiencing a treatment-related adverse event (AE).

POPULATION	The study will enroll up to 10 male and female subjects, ≥ 18 years of age who are seeking non-invasive lipolysis of the flanks.
PHASE	Feasibility
NUMBER OF SITES	one
DESCRIPTION OF DEVICE	The investigational device uses LED technology. The 1060 nm diode laser has been approved by the FDA for non-invasive lipolysis of the flanks.
STUDY DURATION	Two months
PARTICIPANT DURATION	One day plus a telephone follow-up after one week

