### 2.2 RATIONALE

A new emerging technology in the area of aesthetic medicals device is LED (light-emitting diode) photo-modulation. It is currently being used to stimulate fibroblasts to produce collagen and to destroy bacteria on the skin. In this study, a 950 nm LED investigational device is being evaluated to determine if it is able to target adipocytes by maintaining a controlled temperature of 42-47 °C, similar to the reference device. In addition, the safety of the LED device will be compared to the reference device.

The use of this LED device has been determined to present non-significant risk for the intended use in this study, because the device is not:

- Intended as an implant and presents a potential for serious risk to the health, safety, or welfare of a subject;
- Is purported or represented to be for use supporting or sustaining human life and presents a potential for serious risk to the health, safety, or welfare of a subject;
- Is for a use of substantial importance in diagnosing, curing, mitigating, or treating disease, or otherwise preventing impairment of human health and presents a potential for serious risk to the health, safety, or welfare of a subject; or
- Otherwise presents a potential for serious risk to the health, safety, or welfare of a subject.

This study will be conducted in compliance with the protocol and according to Good Clinical Practice standards.

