### 6.2 STUDY DEVICE ACCOUNTABILITY PROCEDURES

The device will be shipped to the site by the sponsor. The device will be labeled as an investigational device and will require protocol and device training from the sponsor.

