#### **Treatment**

Based on the mild nature of treatment, anesthesia is not required. Treatment procedure should include positioning of the patient in a manner that enables access to the target treatment anatomical site. A water-based spray should be applied to the treatment area immediately prior to treatment.

Each subject will receive two consecutive treatments in the following order: the left flank of the abdomen will be treated with the diode laser device and the right flank of the abdomen will be treated with the LED device. The exact placement on the flank will be left to the principal investigator's judgement based on his assessment of individual subject requirements for treatment. Subjects will be treated on the same bilateral location with each device to ensure consistency of measurements. Both laser and LED applicators will be set to same output power level. Two levels will be used 41W (1.17W/cm^2) and 29W (0.83W/cm^2). The first level of 41W corresponds to initial heating for 4 minutes and the second level corresponds to duty cycle of 25 sec on and 10 sec off time. Total treatment time with each device will be 24 minutes (first 4 min at full power and next 16 min at duty cycle 25/10). Both device applicators have same output window dimensions and area 7x5 cm (35 cm^2). Both applicators are cooled by water chiller and therefore provided the same surface cooling temperature on skin.

Immediately (within 2 minutes) after treatment, 3 sterile thermocouple needles of different lengths (7-15 mm), will be inserted into the center of each applicator footprint. Temperature readings from each thermocouple needle will be recorded.

During treatment, subject reaction must be monitored and if the subjects verbally report an intolerable level of pain, treatment shall be ceased immediately.

The normal response to these treatments is transient erythema and edema. If any side effects occur other than a normal transient response, as indicated in the protocol, they will be recorded.

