## 8.4 REPORTING PROCEDURES

### 8.4.1 ADVERSE EVENT REPORTING

All AEs will be recorded on the appropriate CRF and will include information about the start and stop dates, severity and relatedness. There should be an attempt to report a "diagnosis" rather than the individual signs, symptoms and abnormal laboratory values associated with the diagnosis. However, a diagnosis should be reported only if, in the Investigator's judgment, it is relatively certain (i.e., definite or possible). Otherwise individual signs, symptoms and abnormal laboratory values should be reported as distinct adverse events.

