#### 10.4 SAMPLE SIZE

Since this is a feasibility study, no formal sample size calculation is required. The study will recruit up to 10 subjects.

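### The adverse-event rules ask for one relatedness judgement per event and no flank or device, so the treatment-related AE endpoint cannot deliver the planned LED-versus-laser safety comparison

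*Combined protocol and SAP*

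**What the plan says.** The Protocol Summary gives part of the objective as "to compare safety in the treatment of lipolysis of the flanks", and section 2.2 says that "the safety of the LED device will be compared to the reference device". One of the two safety endpoints (section 4.2.2) is the number of subjects with a treatment-related AE; the other is pain on a visual analog scale (VAS).

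Under Treatment in section 7.3.2, "Each subject will receive two consecutive treatments in the following order". The laser goes on the left and the LED on the right, with side and order the same for every subject. No interval between the two treatments is given.

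Section 8.2.2 sets the attribution rule: "All AEs must have their relationship to study agent assessed. In a clinical trial, the study product must always be suspect". The answer is Related or Not Related, and a temporal relationship is enough for Related. Section 8.3 asks for event description, onset, severity, relationship to the study product, and resolution. Section 8.4.1 says that the AE record "will include information about the start and stop dates, severity and relatedness". Neither list names the flank or the device.

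Section 10.3 summarises AEs as the number and percentage of subjects with any AE, with any SAE, and withdrawn because of an AE. It mentions each device separately only for the temperature readings. On size, section 10.4 says: "Since this is a feasibility study, no formal sample size calculation is required. The study will recruit up to 10 subjects".

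**The concern.** A single relatedness question suits a study in which each subject receives one product. Here each subject receives two, and the question of interest is which of them produced the event. One Related / Not Related answer to an undefined singular agent does not carry that information, and the per-subject summaries in section 10.3 do not add it.

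At stake is one of the two safety endpoints. The study could finish with a complete AE listing and still be unable to say how many subjects had a related event on the LED side and how many on the laser side. Causality is judged when the event is assessed. If no judgement is made for each device then, a later table split by device has nothing to draw on. This matters most for events without a side and for events first reported at the telephone contact (section 7.3.3), where nobody examines the skin.

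**Working it through.** The plan gives no power, error rate, event rate or margin, so it has no figure to reproduce. The check asks what the planned AE data can say about a device difference.

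**Inputs from the protocol**
- Up to 10 subjects (section 10.4).
- Both devices in every subject, on fixed sides (section 7.3.2).
- One relationship judgement per event (sections 8.2.2, 8.3 and 8.4.1).
- No flank or device among the listed AE items (sections 8.3 and 8.4.1).
- AE counts per subject (section 10.3).

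**Step 1: bound on the device difference.** Let k of n = 10 subjects have a treatment-related AE, with the device not recorded. Each affected subject had an event from the LED, the laser or both. Each device's own count can therefore be anything from 0 to k, and

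-k/n ≤ (LED rate - laser rate) ≤ +k/n.

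| k of 10 | LED count | Laser count | Possible difference (percentage points) |
|---|---|---|---|
| 1 | 0 to 1 | 0 to 1 | -10 to +10 |
| 3 | 0 to 3 | 0 to 3 | -30 to +30 |
| 5 | 0 to 5 | 0 to 5 | -50 to +50 |

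For k = 3, three LED-only subjects give 3/10 - 0/10 = +30 points. Three laser-only subjects give 0/10 - 3/10 = -30 points. Three subjects with events from both devices give 0. The per-subject summary is 3/10 in all three cases.

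**Step 2: the same point in expected rates.** The documents give no rates, so those below are assumed. If events on the two flanks are independent,

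P(subject has any event) = 1 - (1 - p_laser)(1 - p_LED).

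- Laser 10%, LED 30%: 1 - 0.9 × 0.7 = 37%.
- Laser 30%, LED 10%: 1 - 0.7 × 0.9 = 37%.
- Both 20%: 1 - 0.8 × 0.8 = 36%.

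Without independence, the probability lies between max(p_laser, p_LED) and min(1, p_laser + p_LED). For the 10%/30% pair in either order, that is 30% to 40%. The subject-level rate cannot tell a 20-point LED excess from a 20-point laser excess, and barely differs from the equal-rate case.

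**Step 3: what can be recovered.**
- *Local event with the side written down:* the exposed device follows from the fixed assignment (left = laser, right = LED).
- *Local event reported by telephone without a side:* not assignable unless someone asks.
- *Non-local event after both treatments:* it has no side, and the temporal criterion in section 8.2.2 fits both devices.

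The bound in step 1 therefore applies in full only when no side is recorded. It narrows with each event that can be traced.

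**The case against.** The strongest reply is that much of the information will exist anyway. All AEs are documented whether related or not (section 8.3), and section 8.2.2 says that relatedness does not decide what is reported. The expected events in section 8.2.3 are almost all local skin reactions, and with fixed sides an event description that names the flank identifies the device. The lists in sections 8.3 and 8.4.1 may not be exhaustive, and the AE form itself is not in the documents, so it may already have a body-site field. Burns require the chart and treatment parameters to be forwarded (section 7.8), and SAE reports need a full description. VAS pain is scored after treatment and before any subsequent one, so it can be separated by device. This is also a descriptive study of at most 10 subjects.

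Most of this stands, and it limits the problem for local events. It does not remove it: nothing requires the side to be written, non-local events have none, and section 10.3 plans no AE table by device.

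A reader might go further and infer that *study agent* means the LED alone, because section 6.2 says of the sponsor's unit that "The device will be labeled as an investigational device". Laser-flank events would then either drop out of the related count or be charged to the LED. The documents do not support this. No passage limits the term to the LED; section 4.1 describes the study as evaluating both devices, and the heading of section 6.1 covers device and control. The labelling sentence concerns accountability, not attribution. If the term covers both devices, events are pooled rather than dropped or mischarged. No AE summary in section 10.3 is filtered by relatedness, so laser events would not vanish from the planned tables either.

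**Conclusion.** The concern holds as a gap in attribution and summary. The protocol promises a between-device safety comparison in a split-body design, but requires one relatedness judgement to an undefined agent, lists no flank or device among the AE items, and counts AEs per subject. Followed as written, the treatment-related AE endpoint does not yield the comparison.

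Its size is the width of what stays unknown: from -k/10 to +k/10 when k of 10 subjects are affected and the device is not recorded. With fewer subjects, the denominator is the number treated. This rests on no side being available from the event description; where sides are written down, the uncertainty shrinks to the untraced events. The rates in step 2 of the working are assumptions for scale only.

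This does not show a bias for or against either device; the direction of any bias is unknown. Nor does it show that laser events go unrecorded, or that the two treatments are a particular number of minutes apart: the protocol says only that they are consecutive.

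**What to change.** 1. In sections 8.2.2, 8.3 and 8.4.1, replace the single relationship to the study agent or study product with two judgements for every AE: relationship to the LED device and relationship to the diode laser device. Apply the same Related / Not Related definitions to both.
2. Record the AE location on the AE form (left flank, right flank, both, non-local), and ask for it at the telephone contact in section 7.3.3.
3. In section 10.3, tabulate treatment-related AEs by device as paired within-subject data (neither, LED only, laser only, both). List events judged related to both devices separately.

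The cost is a location field and a second relationship field on the AE form, wording changes in three safety sections, and one added table. No extra subjects or visits are needed. A small downside is that some non-local events will be recorded as related to both devices.
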